### **11.2.2 Serious Adverse Events (Including Deaths) and Adverse Events Leading to Study Drug Discontinuation**

All TESAEs, deaths, and TEAEs leading to discontinuation of study drug will be summarized. The number and percentage of subjects experiencing SAEs (including deaths) and adverse events leading to discontinuation of study drug will be tabulated by SOC and PT for each treatment group.

### **11.2.3 Listing of Adverse Events**

The following additional summaries will be provided for treatment-emergent adverse events, unless otherwise specified.

- List of subject numbers associated with each PT for TEAEs.
  - List of subject numbers associated with each PT for TEAEs assessed by the investigator as reasonable possibility of being related to study drug.
  - Listing of pretreatment AEs.
  - Listing of TESAEs.
  - Listing of TEAEs that led to discontinuation of study drug.
  - Listing of all deaths.
  - Listing of treatment-emergent AESIs.
-

### 11.3 Analysis of Laboratory Data

For the assessments of laboratory data, values observed more than 30 days after the last dose of study drug will be excluded.

All laboratory parameters to be collected in this study are listed in [Table 16](#) below. Laboratory parameters will be reported using the standard international (SI) units.

**Table 16. List of Laboratory Variables**

Hematology	Chemistry	Urinalysis
White Blood Cell (WBC) Count	Total Bilirubin	Specific Gravity
Red Blood Cell (RBC) Count	Alkaline Phosphatase (ALP)	pH
Hemoglobin	Serum glutamic oxaloacetic transaminase (SGOT/AST)	Protein*
Hematocrit	Serum glutamic pyruvic transaminase (SGPT/ALT)	Glucose*
Platelets count	Total Protein	Ketones*
Neutrophils	Albumin	Blood*
Basophils	Glucose	Nitrite*
Eosinophils	Triglycerides	Microscopic Examination*
Lymphocytes	Blood Urea Nitrogen (BUN)	
Monocytes	Creatinine	Other
Reticulocytes*	Uric acid	hsCRP
Bands	Sodium	HBs Ab*
	Potassium	HBc Ab*
	Calcium	Hbs Ag*
	Inorganic Phosphorus	HBV DNA PCR reflex only*
	Creatine Phosphokinase (CPK)	HCV Ab*
	Chloride	HCV RNA reflex only*
	Bicarbonate	QuantiFERON-TB Gold*
	Cholesterol	
	LDL cholesterol	
	HDL cholesterol	

\* The parameters will only be presented in data listing.

#### 11.3.1 Variables and Criteria Defining Abnormality

Criteria for Potentially Clinically Significant chemistry and hematology variables are listed in [Table 17](#) below.

**Table 17. Definitions of Potentially Clinically Significant Chemistry and Hematology Variables Based on CTCAE Grades**

Test	Grade 1	Grade 2	Grade 3	Grade 4
SGPT/ALT	> ULN – 3.0 × ULN	> 3.0 – 5.0 × ULN	> 5.0 – 20.0 × ULN	> 20.0 × ULN
SGOT/AST	> ULN – 3.0 × ULN	> 3.0 – 5.0 × ULN	> 5.0 – 20.0 × ULN	> 20.0 × ULN
ALP	> ULN – 2.5 × ULN	> 2.5 – 5.0 × ULN	> 5.0 – 20.0 × ULN	> 20.0 × ULN
TBL	> ULN – 1.5 × ULN	> 1.5 – 3.0 × ULN	> 3.0 – 10.0 × ULN	> 10.0 × ULN
Creatinine increased	> ULN – 1.5 × ULN	> 1.5 – 3.0 × ULN	> 3.0 – 6.0 × ULN	> 6.0 × ULN
CPK increased	> ULN – 2.5 × ULN	> 2.5 – 5.0 × ULN	> 5.0 – 10.0 × ULN	> 10.0 × ULN
Hemoglobin decreased	< LLN – 100.0 g/L	< 100.0 – 80.0 g/L	< 80.0 g/L	N/A
Neutrophil count decreased	< LLN – 1.5 × 10  /L	< 1.5 – 1.0 × 10  /L	< 1.0 – 0.5 × 10  /L	< 0.5 × 10  /L
WBC decreased	< LLN – 3.0 × 10  /L	< 3.0 – 2.0 × 10  /L	< 2.0 – 1.0 × 10  /L	< 1.0 × 10  /L
Lymphocyte count decreased	< LLN – 0.8 × 10  /L	< 0.8 – 0.5 × 10  /L	< 0.5 – 0.2 × 10  /L	< 0.2 × 10  /L

### **Definitions of Potential Hy's Law Cases**

According to FDA's Guidance for Industry "Drug-Induced Liver Injury: Premarketing clinical evaluation (July 2009), when aminotransferase (AT) abnormalities indicating hepatocellular injury are accompanied by evidence of impaired hepatic function (bilirubin elevation > 2 × ULN), in the absence of evidence of biliary obstruction (i.e., significant elevation of ALP) or some other explanation of the injury (e.g., viral hepatitis, alcohol hepatitis), the combined finding (i.e., Hy's Law cases) represents a signal of a potential for the drug to cause severe DILI.

### **11.3.2 Statistical Methods**

#### **11.3.2.1 Analysis for Continuous Laboratory Data**

Mean changes from baseline in all continuous laboratory parameters in each visit in Period 1 will be summarized with the number of observations, mean, standard deviation and median. The treatment comparison between groups will be using a one-way ANOVA. Percent change from baseline for selected lab parameters will also be summarized. Summaries for the baseline and final value will be presented for subjects

who have both baseline and post-baseline values. Categorical data will be summarized using frequencies and percentages.

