Period 2 will begin after the Week 16 Visit and will end at the Week 88 Visit. At the Week 16 Visit, subjects will be re-randomized as described in Section 5.1. During Period 2 of the study, subjects will visit the study site at Weeks 20, 24, 32, 40, 52, 64, 76, and 88. A \pm 5 day window is permitted around scheduled study visits. Subjects will start on their assigned treatment at the Week 16 visit.

The last dose of study drug is taken the day prior to the Week 88 visit.

Twice daily use of an additive-free, bland emollient is required throughout Period 2.

Discontinuation of Study Drug and Continuation of Study Participation

Subjects may discontinue study drug treatment, but may choose to continue to participate in the study (refer to Section 5.4.1 for additional details). Subjects who prematurely discontinue study drug should complete a Premature Discontinuation Visit (PD visit) as soon as possible, preferably within 2 weeks. Afterwards, subjects should follow the regular visit schedule as outlined in Table 2 and adhere to all study procedures except for dispensing study drug, PK sample collection, and blood and skin biopsy sample collection for optional exploratory research and validation studies. In addition, all future rescue and efficacy-driven discontinuation criteria no longer apply.

In Period 1, discontinuation from study drug will be mandatory for any subject with an EASI score worsening of 25% or more compared with their Baseline EASI score at any 2 consecutive scheduled study visits from Week 4 to Week 12.

In Period 2, discontinuation from study drug will be mandatory for subjects with < EASI 50 response compared with their Baseline EASI score 4 weeks following rescue with topical corticosteroids or at any visit thereafter.

Premature Discontinuation of Study (Withdrawal of Informed Consent)

Subjects may withdraw from the study completely (withdrawal of informed consent) for any reason at any time (refer to Section 5.4.2 for additional details). If a subject prematurely discontinues study participation (withdrawal of informed consent), the procedures outlined for the Premature Discontinuation visit (PD visit) should be completed as soon as possible, preferably within 2 weeks of study drug discontinuation. In addition, if the subject is willing, a 30-day follow-up visit (or phone call if a visit is not possible) may occur to determine the status of any ongoing AEs/SAEs or the occurrence of any new AEs/SAEs.

Follow-Up Period

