8.1.6.3 Analysis of Laboratory, Vital Sign, and ECG Data

Changes from baseline by visit, and changes from baseline to minimum value, maximum value, and final values in continuous laboratory data, and vital signs will be summarized by treatment group.

The laboratory data will be categorized as low, normal, or high based on the normal ranges of the laboratory used in this study. The shift tables will tabulate the number and percentage of subjects with baseline values below/within/above the normal range versus minimum/maximum/final values below/within/above the normal range. Shift tables for

liver elevations from baseline to post baseline maximum value will be summarized for each treatment group.

Listings will be provided for potentially clinically significant laboratory values and vital signs.

Analysis details will be specified in the SAP.

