### **Definition of Final Observation for Safety Analysis**

**Period 1:** The final observation is defined as the last non-missing observation collected

- within 30 days following the last dose of study drug in Period 1 for subjects who discontinued from the study drug without having any dose of study drug in Period 2,
- on or before the day of the first dose of study drug in Period 2 for subjects who had at least one dose of the study drug in Period 2.

Laboratory and vital sign evaluations performed on the day of the first dose of study drug in Period 2 will be included in the analysis for Period 1. AEs with onset on the date of the first dose of Period 2 will be attributed to Period 1.

**Period 2:** The final Observation in each period is defined as the last non-missing observation collected within 30 days following the last dose of study drug in the respective period.

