**Table 7. Analysis Windows for EASI, SCORAD, IGA, BSA, PGIS, Laboratory Parameters and Vital Sign Variables (Period 2)**

Scheduled Week	Nominal Day	P2 Rx Day Interval
Entry of Period 2 (Week 16)	1	$\leq 1$
Week 20	29	2 – 43
Week 24	57	44 – 85
Week 32	113	86 – 141
Week 40	169	156 – 211
Week 52	253	212 – 295
Week 64	337	296 – 379
Week 76	421	378 – 463
Week 88	505	464 – 546

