## **11.0 Safety Analysis**

### **11.1 General Considerations**

Safety analyses will include adverse events, laboratory, and vital sign measurements. Safety summaries will be provided using the safety population in each period. Comparison between each upadacitinib group and placebo group will be performed for change from baseline laboratory and vital sign parameters in the Safety\_1 Population, using one-way ANOVA.

Missing safety data will not be imputed.

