### **11.3.2.3 Potentially Clinically Significant Laboratory Values**

Criteria for identify Potentially Clinically Significant laboratory values are listed in the table above. Of note, a post-baseline value has to be more extreme than baseline value to be considered.

Frequencies and percentages of subjects with post Baseline lab values that are Grade 3 or above according to the CTC toxicity criteria, will be summarized. A listing of the subjects with laboratory values that are CTC toxicity Grade 3 or above will be provided. For each of these subjects, the whole course of the respective parameter will be listed.

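### SAP 11.3.2.1, as worded, confines by-visit laboratory means to Period 1 and omits change to minimum and maximum, in undeclared conflict with Protocol 8.1.6.3 and at odds with other SAP text

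*SAP*

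**What the plan says.** Protocol 8.1.6.3 plans "Changes from baseline by visit, and changes from baseline to minimum value, maximum value, and final values in continuous laboratory data, and vital signs", summarised by treatment group. It sets no period limit, and Protocol 8.1.6.1 places the safety analyses in each period.

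SAP 11.3.2.1 is narrower: "Mean changes from baseline in all continuous laboratory parameters in each visit in Period 1 will be summarized". It then gives a one-way ANOVA between groups and summaries of the baseline and final value. It mentions no change to minimum or maximum. For vital signs, SAP 11.4.2 summarises change at post-baseline visits without a period limit and ties only the ANOVA to Period 1, but it names no change to minimum, maximum or final value.

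Other parts of the SAP point towards Period 2 output:
- Section 11.1: "Safety summaries will be provided using the safety population in each period". Only the test is restricted to Safety_1: "Comparison between each upadacitinib group and placebo group will be performed for change from baseline laboratory and vital sign parameters in the".
- Table 7 sets Period 2 analysis windows for laboratory parameters at all eight visits.
- Section 6.0 gives Period 2 its own endpoint: "The final Observation in each period is defined as the last non-missing observation collected within 30 days following the last dose of study drug".

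SAP 12.1 lists four departures from the protocol: baseline tests, the quadratic model, DLQI, and a pruritus endpoint. None concerns laboratory or vital-sign summaries.

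**The concern.** SAP 3.0 says the document is there to guide programming. The section that defines the continuous laboratory tables is therefore the one a programmer will follow, and as written it stops at Week 16. The protocol named these summaries and did not stop there, and the change is not declared.

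Protocol 5.6.1 gives longer-term safety as one purpose of Period 2. By-visit group means are the output that shows when a laboratory value begins to move and whether it settles. Without them, a gradual change in a group mean over Weeks 20 to 88 could be visible only through its final value or through the subjects who cross a grade boundary.

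**Working it through.** The plan states no figure on this point to reproduce. The check is a visit count, a comparison of sections, and a check of the window tables.

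**1. Visit count.** Inputs: Protocol 5.1 and Table 2, Note 1.
- Period 1: Weeks 2, 4, 8, 12, 16 = 5 visits.
- Period 2: "subjects will visit the study site at Weeks 20, 24, 32, 40, 52, 64, 76, and 88" = 8 visits.
- Share with no by-visit laboratory summary on the literal reading: 8 / (5 + 8) = 8/13 = 61.5%.
- Weeks covered by those visits: 88 − 16 = 72, and 72/88 = 81.8% of treatment time.

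The count leaves out the premature-discontinuation, post-topical-rescue and 30-day follow-up visits. Protocol Table 2 schedules laboratory tests at all eight Period 2 visits, so the data will exist.

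**2. Version check.** SAP 3.0 refers to the protocol of 07 June 2017. Appendix Q of the current protocol itemises changes to 6.1.1.3 and 8.1.6.2.1 only. Section 8.1.6.3 was not altered, so timing does not explain the difference.

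**3. Side by side.**

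| Output | Protocol 8.1.6.3 | SAP |
|---|---|---|
| Laboratory change by visit | Yes, no period limit | Period 1 only (11.3.2.1) |
| Laboratory change to minimum, maximum | Yes | Not named |
| Laboratory final value | Change to final | Baseline and final value summarised (11.3.2.1) |
| Vital-sign change by visit | Yes | Yes, no period limit (11.4.2) |
| Vital-sign change to minimum, maximum, final | Yes | Not named |

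Minimum and maximum do appear in SAP 6.0, but only for shift summaries and listings.

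**4. What Period 2 still has.** The shift tables (11.3.2.2), Grade 3 or above counts and listing (11.3.2.3) and liver categories (11.3.2.4) carry no Period 1 limit. For subjects reaching Grade 3 or above: "For each of these subjects, the whole course of the respective parameter will be listed". Table 17 grades haemoglobin, lymphocytes, CPK and creatinine from Grade 1, so Grade 1 and 2 movement in these is described in both periods. Table 17 has no limits for lipids or platelets, although Table 16 lists both.

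**5. Rescue.** From Week 20, subjects on placebo, 7.5 mg or 15 mg with less than an EASI 50 response move to 30 mg for the rest of the study. SAP 5.1 assigns the as-treated group by the dosage received most in the period. A completer rescued at Week 20 has 20 − 16 = 4 weeks on the assigned treatment and 88 − 20 = 68 weeks on 30 mg. If that rule is applied to rescued subjects, the Week 20 value, obtained on the lower dose or placebo, is counted under 30 mg. Period 2 means by as-treated group would mix doses.

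**6. Analysis windows (a separate defect).** Nominal day = (week − 16) × 7 + 1, giving Week 32 = 113, Week 40 = 169, Week 64 = 337, Week 76 = 421. The other Table 7 boundaries start a window on the day after the midpoint.
- Weeks 32 and 40: (113 + 169)/2 = 141, so Week 40 should start on Day 142. Table 7 has 156, which leaves Days 142–155 (14 days) in no window.
- Weeks 64 and 76: (337 + 421)/2 = 379, so Week 76 should start on Day 380. Tables 7, 9 and 10 have 378, which puts Days 378–379 in two windows. Table 8 already has 380.
- Visits within ±5 days: Week 32 = 108–118, Week 40 = 164–174, Week 64 = 332–342, Week 76 = 416–426. None is affected.
- A visit 4 weeks after topical rescue at Week 32: 113 + 28 = Day 141, allowed Days 136–146, of which 142–146 (5 of 11 days) fall in the gap.

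**The case against.** The best answer is that the SAP, read whole, does intend Period 2 by-visit laboratory tables. Section 11.1 promises summaries in each period and restricts only the test, as 11.4.2 does for vital signs. The shift, minimum, maximum and final outputs use all values in the treatment-emergent window (SAP 6.0), so by-visit summaries are the evident laboratory use of the Period 2 windows in Table 7. This stands as to intent: the words *in Period 1* were probably meant for the ANOVA. It does not remove the problem, because no section specifies the Period 2 table and the one that should do so excludes it.

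Second, the SAP elaborates the protocol, so not repeating an output does not withdraw it. That has force for minimum and maximum, where the SAP is merely silent, and for the laboratory final value, where only the explicit change is missing. It has none for a stated limit to Period 1. The protocol's deferral to the SAP in 8.1.6.3 covers details, not whether a named summary is produced.

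Third, shift tables already show Grade 1 and 2 movement in the main haematology and chemistry parameters, and an external monitoring committee sees unblinded safety data. This stands and narrows the loss.

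Fourth, rescue blurs Period 2 means. This also stands, and it affects how the tables should be laid out.

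A reader might infer that Period 2 laboratory safety goes unreported, that a signal would be missed, or that the sponsor deliberately cut the analysis. The documents support none of these: several Period 2 laboratory summaries remain, and the surrounding text points to a misplaced phrase.

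**Conclusion.** The point holds as a minor internal inconsistency and an undeclared departure from Protocol 8.1.6.3. On the literal wording, 8 of 13 scheduled post-baseline treatment visits have no specified by-visit laboratory summary. That figure counts visits; it does not measure lost safety information.

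What would be missing is limited to three things: the visit timing of group mean changes over Weeks 20 to 88, mean changes that cross no grade, and the course of parameters that Table 17 does not grade, such as lipids and platelets. The last item assumes that grading is confined to the limits printed in Table 17. No efficacy conclusion changes.

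The window errors are real but add no weight to this point. They touch only unscheduled, premature-discontinuation, post-topical-rescue or out-of-window visits.

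**What to change.** In SAP 11.3.2.1:
- Summarise mean changes *at each visit in Period 1 and Period 2*.
- Add change from baseline to minimum, maximum and final value.
- State that the one-way ANOVA is done in Safety_1 only and that Period 2 is descriptive.

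In SAP 11.4.2, add change to minimum, maximum and final value for vital signs.

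In the Period 2 by-visit tables, present values before and after rescue separately, or flag those after rescue, so that means can be read by the dose being taken.

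As a separate correction, set Week 40 in Table 7 to Days 142–211, and Week 76 in Tables 7, 9 and 10 to Days 380–463.

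The cost is a phrase and a few sentences, the window corrections, and extra runs of an existing table program with a rescue split or flag. No new data are needed.

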### **11.3.2.2 Shift Table Analyses**

Baseline and post-baseline laboratory observations will be categorized as Grade 1, Grade 2, Grade 3, and Grade 4 according to National Cancer Institute Common Toxicity Criteria (NCI CTC) AE version 4.03 grades (publish date: June 14, 2010) (See definition in [Table 17](#)). Shift tables for changes from Baseline according to the NCI CTC toxicity grade will be provided for each hematology, clinical chemistry and urinalysis parameter.

### **11.3.2.3 Potentially Clinically Significant Laboratory Values**

Criteria for identify Potentially Clinically Significant laboratory values are listed in the table above. Of note, a post-baseline value has to be more extreme than baseline value to be considered.

Frequencies and percentages of subjects with post Baseline lab values that are Grade 3 or above according to the CTC toxicity criteria, will be summarized. A listing of the subjects with laboratory values that are CTC toxicity Grade 3 or above will be provided. For each of these subjects, the whole course of the respective parameter will be listed.

### **11.3.2.4 Liver Function Tests**

Additional summaries will be presented for liver function tests including ALT or SGPT, AST or SGOT, alkaline phosphatase, and total bilirubin. Each laboratory value will be categorized as follows:

- $< 1.5 \times \text{ULN}$
  - $\geq 1.5 \times \text{ULN} - < 3.0 \times \text{ULN}$
  - $\geq 3.0 \times \text{ULN} - < 5.0 \times \text{ULN}$
  - $\geq 5.0 \times \text{ULN} - < 10.0 \times \text{ULN}$
  - $\geq 10.0 \times \text{ULN} - < 20.0 \times \text{ULN}$
  - $\geq 20.0 \times \text{ULN}$
-

For the purpose of assessing for potential Hy's law cases, the frequencies and percentages of subjects with post baseline liver specific function test values that meet the following criteria of potential clinical interest should be presented:

- $ALT \geq 3 \times ULN$
- $ALT \geq 5 \times ULN$
- $ALT \geq 10 \times ULN$
- $ALT \geq 20 \times ULN$
- $AST \geq 3 \times ULN$
- $AST \geq 5 \times ULN$
- $AST \geq 10 \times ULN$
- $AST \geq 20 \times ULN$
- $TBL \geq 2 \times ULN$
- Alkaline phosphatase  $\geq 1.5 \times ULN$
- $ALT$  and/or  $AST \geq 3 \times ULN$  and concurrent  $TBL \geq 1.5 \times ULN$
- $ALT$  and/or  $AST \geq 3 \times ULN$  and concurrent  $TBL \geq 2 \times ULN$

## **11.4 Analysis of Vital Signs and Weight**

### **11.4.1 Variables and Criteria Defining Abnormality**

Definition of Potentially Clinically Significant vital signs variables based on Criteria are listed in [Table 18](#) below.

**Table 18. Definition of Potentially Clinically Significant Vital Signs Variables**

Vital Sign	Category	Criteria for Potential Clinically Significant Vital Signs
Systolic blood pressure	Low	Value $\leq$ 90 mmHg and decrease $\geq$ 20 mmHg from Baseline
	High	Value $\geq$ 160 mmHg and increase $\geq$ 20 mmHg from Baseline
Diastolic blood pressure	Low	Value $\leq$ 50 mmHg and decrease $\geq$ 15 mmHg from Baseline
	High	Value $\geq$ 105 mmHg and increase $\geq$ 15 mmHg from Baseline
Pulse	Low	Value $\leq$ 50 bpm and decrease $\geq$ 15 bpm from Baseline
	High	Value $\geq$ 120 bpm and increase $\geq$ 15 bpm from Baseline
Respiratory Rate	Low	< 10 rpm
	High	> 24 rpm
Body temperature	High	> 39.0°C (102.3°F)
Weight	High	> 7% increase from baseline
	Low	> 7% decrease from baseline

#### 11.4.2 Statistical Methods

Changes from Baseline to post-baseline visits will be summarized with the baseline mean, the visit mean, change from baseline mean, standard deviation, and median. An ANOVA model with only treatment as a factor, not controlling for baseline, will be used to test statistical significance for the change from baseline mean, and present confidence intervals for the difference between each of the upadacitinib treatment group and placebo in Period 1. The number and percentage of subjects meeting the criteria for potentially clinically significant vital sign values will be summarized.

Vital sign results satisfying the criteria for potentially clinically significant vital sign findings will be identified in a listing. Of note, a post-baseline value has to be more extreme than baseline value to be considered.

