8.1.2 Planned Methods of Statistical Analysis

Unless otherwise specified, all statistical tests will be two-sided significance level of 0.05. A test will be deemed significant if the *P* value rounded to three decimal places is less than or equal to 0.050 unless otherwise specified. Descriptive statistics will be provided including the number of observations, mean, median, standard deviation, minimum, and maximum for continuous variables, and counts and percentages for discrete variables.

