8.1.6 Safety Analysis

8.1.6.1 General Considerations

Safety analyses will be carried out using the Safety Population, in each period, and is based on treatments actually received. Safety will be assessed by AEs, physical examination, laboratory assessments, ECG, and vital signs. Frequency tables and lists of subjects with treatment-emergent AEs by preferred term as in the Medical Dictionary for Regulatory Activities (MedDRA) dictionary, by system organ class, by severity, and by relationship to the study drug as assessed by the Investigator will be provided. The changes from baseline in vital signs, physical examination results, and clinical laboratory values will be analyzed in a descriptive manner. Shift of laboratory values from baseline to defined time points will be tabulated.

Missing safety data will not be imputed.

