### **10.1.2 Analysis of Continuous Variables**

For continuous variables, the model based mean and standard error will be provided. The Baseline and visit means will also be presented for each treatment group. The treatment groups will be compared using the analysis of covariance (ANCOVA) model with treatment group and stratification factors as fixed effects, and the corresponding baseline value as covariates. Point estimates and 95% CIs of mean change from baseline within treatment groups, and between each upadacitinib treatment group and placebo will be provided.

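### Laboratory and vital-sign change is compared with placebo without a baseline covariate: valid on average, but less precise than ANCOVA and sensitive to chance baseline imbalance

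*SAP*

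**What the plan says.** Three SAP sections set the model.

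- SAP 11.1 fixes the scope: "Comparison between each upadacitinib group and placebo group will be performed for change from baseline laboratory and vital sign parameters", in the Period 1 safety population, "using one-way ANOVA".
- SAP 11.3.2.1 repeats it for continuous laboratory data: "The treatment comparison between groups will be using a one-way ANOVA". It names no confidence interval.
- SAP 11.4.2 is the most explicit, for vital signs: "An ANOVA model with only treatment as a factor, not controlling for baseline, will be used to test statistical significance". It also undertakes to "present confidence intervals for the difference between each of the upadacitinib treatment group and placebo in Period 1".

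No safety section offers a baseline-adjusted alternative or a reason for leaving baseline out.

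Two other places bear on this. For continuous efficacy variables, SAP 10.1.2 uses ANCOVA with "treatment group and stratification factors as fixed effects, and the corresponding baseline value as covariates". Protocol 8.1.6.1 did not plan safety tests on these data at all: "The changes from baseline in vital signs, physical examination results, and clinical laboratory values will be analyzed in a descriptive manner". The protocol synopsis says the same for vital signs and laboratory values. SAP 12.1, which records departures from the protocol, does not mention the added tests.

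**The concern.** The covariate is already available. Protocol Table 2 schedules laboratory tests and vital signs at Screening and Baseline, and SAP 6.0 defines the baseline value. Leaving it out of a model for change has two costs. The residual variance is larger than it need be. In addition, if one arm happens to start higher on a parameter, its mean change is pulled downwards relative to placebo by an amount unrelated to drug.

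Anaemia, neutropenia, decreased lymphocyte counts and CPK elevation are adverse events of special interest in this dose-ranging study (Protocol 6.1.1.3). With about 40 subjects per arm, mean change is one of the places where a dose-related shift could appear or be blurred. Protocol 8.1.2 says that, unless otherwise specified, "all statistical tests will be two-sided significance level of 0.05", so the resulting P values will be read against that level.

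**Working it through.** **Inputs.** About 40 subjects per arm, four arms, 1:1:1:1 (Protocol 8.2 and 8.3). Model: change = follow-up − baseline, treatment only (SAP 11.1, 11.3.2.1, 11.4.2). The correlation r between baseline and follow-up is not in the documents. I assume 0.5 to 0.95, with equal SD s at both times.

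**The plan's own figure.** The documents state no power or precision for these comparisons. Their only pairwise power is for percent change in EASI (97% and 78%). A noncentral t calculation with 40 per arm and SD 40 gives 97.2% for a difference of 35 and 78.8% for a difference of 25. The stated figures are reproduced, but they do not bear on this point.

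**Precision.** Per subject:

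- ANOVA on change: variance 2s²(1 − r).
- ANCOVA: variance s²(1 − r²).
- Ratio ANCOVA/ANOVA = (1 − r²) / [2(1 − r)] = (1 + r)/2.
- Interval width, ANOVA relative to ANCOVA = √[2/(1 + r)].
- Subjects per arm that the planned ANOVA would need to match ANCOVA with 40 = 40 / [(1 + r)/2].

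**Baseline imbalance.** For a baseline difference D between two arms, the expected follow-up difference without drug effect is rD. The expected difference in change is therefore rD − D = −(1 − r)D. The chance difference D has SD √(2/40) = 0.224 baseline SD, and a 95% range of ±1.96 × 0.224 = ±0.44 SD. The last column gives the size of the shift when D equals 0.224 SD.

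| r (assumed) | Variance ratio | Variance cut by ANCOVA | Width ratio | Equivalent n per arm | Shift, in SD |
|---|---|---|---|---|---|
| 0.5 | 0.75 | 25% | 1.155 | 53 | 0.112 |
| 0.6 | 0.80 | 20% | 1.118 | 50 | 0.089 |
| 0.7 | 0.85 | 15% | 1.085 | 47 | 0.067 |
| 0.8 | 0.90 | 10% | 1.054 | 44 | 0.045 |
| 0.9 | 0.95 | 5% | 1.026 | 42 | 0.022 |
| 0.95 | 0.975 | 2.5% | 1.013 | 41 | 0.011 |

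The shift can also be set against the standard error of the contrast itself. An imbalance at the 1.96 limit moves the change-score contrast by 1.96 × √[(1 − r)/2] of its standard error: 0.98 at r = 0.5, 0.62 at r = 0.8 and 0.44 at r = 0.9.

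**Simulation check** (four arms of 40, 4,000 replicates per r, no drug effect). At r = 0.3, 0.5, 0.7 and 0.9:

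- The width ratios were 1.236, 1.151, 1.081 and 1.023.
- The slope of the ANOVA contrast on the imbalance was −0.724, −0.504, −0.282 and −0.100, against −(1 − r) in theory.
- The slope of the ANCOVA contrast was −0.023, −0.001, 0.018 and 0.000.

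Type I error of the ANOVA lay between 0.047 and 0.050 over these values and r = 0.98. At r = 0.98 the width ratio was 1.002, so ANCOVA did not lose precision even there.

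**How often imbalance will occur.** SAP Table 16 has 11 haematology and 21 chemistry parameters that are not restricted to listings. Three doses against placebo give 32 × 3 = 96 baseline contrasts, of which 0.05 × 96 ≈ 5 are expected beyond 1.96 standard errors by chance.

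**The case against.** The strongest defence is that nothing here is invalid. In a randomised comparison, ANOVA on change is unbiased over randomisations and holds its error rate, as the simulation shows. The SAP states the choice openly and consistently. These are Phase 2b safety comparisons without multiplicity adjustment (SAP 10.6), and no decision rule rests on them. That all stands, and it is why the point is an efficiency gain and not a correction of an error.

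Several stronger readings are tempting, and the documents do not support them.

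- A reader might infer that baseline imbalance goes entirely uncorrected. It does not. Subtraction adjusts with a fixed slope of 1, which is too much when the true slope is below 1.
- A reader might infer that regression to the mean biases the comparison. Under randomisation it is equal across arms in expectation, so the shift is conditional on a chance imbalance.
- A reader might extend the interval finding to laboratory data. Intervals, and the explicit statement about not controlling for baseline, appear only in the vital-signs section. For laboratory data the omission follows from the one-way model, and the cost is test precision.
- A reader might infer that haematology or CPK signals would be missed. The SAP also has CTCAE-graded shift tables (11.3.2.2), counts and listings of Grade 3 or above (11.3.2.3) and summaries of adverse events of special interest (11.2.1.6). A data monitoring committee reviews unblinded safety data (4.4). None of these uses the ANOVA. Of the laboratory parameters usually watched, lipids rely most on mean change, since Table 17 does not grade them.
- A reader might infer that the primary efficacy analysis adjusts for baseline and the safety analysis alone does not. SAP 10.1.2 covers continuous variables in general. The sections on the primary MCP-Mod analysis (10.1.4 and 10.3) name no baseline covariate.

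The size is also assumption-driven. At r of 0.9 or more the variance saving is 5% or less.

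**Conclusion.** The point holds as a low-priority improvement. The planned comparison is valid on average, but it gives up precision and lets a chance baseline imbalance through with weight −(1 − r). The loss ranges from a quarter of the variance at r = 0.5 to 2.5% at r = 0.95.

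This rests on an assumed r and on equal SDs at baseline and follow-up. If the SDs differ, the loss depends on how far the regression slope of follow-up on baseline is from 1, and a slope above 1 would turn over-correction into under-correction. I am confident about the model specified and the direction of the effect, and less so about its size, which will vary by parameter.

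The omission from SAP 12.1 is a separate, documentary matter and needs no assumption. The protocol supplied is dated a week after the SAP (30 August against 23 August 2017). Its list of changes touches only adverse events of special interest, so it did not introduce the descriptive wording.

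**What to change.** In SAP 11.1, 11.3.2.1 and 11.4.2, replace the one-way ANOVA by ANCOVA on change from baseline, with treatment as a factor and the baseline value of the same parameter as covariate. Report the adjusted differences from placebo. In SAP 12.1, add a line saying that tests of laboratory and vital-sign change were added to the descriptive analysis planned in the protocol.

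If the sponsor prefers not to test these data, returning to descriptive summaries as in Protocol 8.1.6.1 is also coherent. The tests should then be removed from all three sections.

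The cost is a few lines of SAP text and one model term. No new data are needed, and the graded shift tables, threshold counts and adverse-event summaries stay as they are.
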